11.1.6 Vital Signs

Orthostatic vital signs including pulse, blood pressure, and body temperature will be measured at the times indicated in [Table 2](#). Temperature measurements should be assessed by a consistent method (e.g. all oral or all ear [tympanic membrane] measurements) and by the same method as baseline, if baseline is available. Weight will be measured at the times indicated in [Table 2](#).

Systolic blood pressure (SBP), diastolic blood pressure (DBP) and pulse rate are to be measured while the subject is supine (after 3 to 5 minutes) and standing (after 2 minutes).

11.1.7 Physical Examination

A physical exam as per usual practice will be performed at 6 month intervals, and at the time of the subjects' termination from the study. Any relevant findings are to be recorded on the Adverse Events Form in the eCRF.

11.1.8 Neurological Examination

A Neurologic Examination including light touch and pinprick sensation, vibratory sensation, deep tendon reflexes, and strength assessments will be performed at the times indicated in [Table 2](#). The Neurologic Examination will be done during "On" time.

Any abnormalities or symptoms identified during treatment will be recorded as adverse events.

The neurological examination will assess:

- Cranial nerves – assessment of cranial nerves II–XII, excluding fundoscopic examination
- Motor system – assessment of tone, strength and abnormal movements
- Sensory system – including light touch, pinprick, joint position and vibratory sense
- Reflexes – assessment of deep tendon reflexes and plantar responses (Babinski sign)
- Coordination – assessment of upper and lower extremities
- Gait – assessment of base and tandem gait
- Station – assessment of posture and stability

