 - a. The final assessment in the previous open-label LCIG study will serve as the baseline assessment for this item.
 - b. Will be done as clinically indicated.
 - c. For women of childbearing potential.
 - d. Assessment performed once yearly.
 - e. Clinical supply visits should take place every 6 weeks \pm 7 days. These visits may take place at the hospital pharmacy and are for the purpose of dispensing clinical study drug and ancillary supplies. Other assessments may be completed during these visits if required. When scheduling the 6 weekly drug dispensing visits, the site should always refer back to the baseline visit. Every attempt should be made to pick up drug on the original targeted dates (\pm 7 days).
 - f. The "Already Enrolled Subjects" C-SSRS is to be the first assessment scale administered to the subject. At each subsequent assessment, the "Since Last Visit" C-SSRS scale should be administered. If the subject has previously completed the "Already Enrolled Subjects" scale in the S187.3.003 study, the subject should complete the "Since Last Visit" scale at all scheduled time points outlined in [Table 2](#) in this study. For subjects with a C-SSRS completed at their S187.3.003 final visit, that S187.3.003 final visit C-SSRS assessment will be considered baseline for the S187.3.005 study. For all other subjects, the first C-SSRS assessment completed in this study will serve as baseline.
 - g. The Daily Dosing Diary and the Parkinson's Disease Diary will be completed by subjects or their caregivers for the 3 consecutive days prior to each clinic visit at US sites only.
 - h. The UPDRS and the PDQ-39 will be completed at US sites only.

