13.3 Statistical Methods

Safety Analysis

The Safety Population will be used for the analysis of the safety and tolerability data.

Adverse events will be coded using the Medical Dictionary for Regulatory Activities (MedDRA). A treatment-emergent adverse event (TEAE) is defined as any adverse event that begins or worsens in severity on or after the first dose of study drug in the current study and within 30 days of the end of LCIG treatment in the current study. For subjects transferring to commercial product, the end of treatment in the current study will be the last dose of study drug. For subjects who are discontinuing LCIG treatment, the end of treatment in the current study will be the removal of the PEG-J tube. The following summaries of TEAE's will be prepared:

- Incidence of treatment-emergent adverse events
- Incidence of treatment-emergent serious adverse events

- Incidence of treatment-emergent adverse events resulting in study termination
- Incidence of treatment-emergent adverse events of special interest

The following additional analyses of safety will also be prepared:

- Summary of vital sign and weight values and mean change from Baseline over time
- Incidence of potentially clinically significant vital sign and weight values
- Summary of clinical lab values and mean change from Baseline to Endpoint
- Summary of special lab values and mean change from Baseline over time
- Incidence of potentially clinically significant clinical lab values
- Summary of MIDI at Baseline and during treatment
- Summary of C-SSRS
- Incidence of device complications

Efficacy Analysis

The Efficacy Population will be used for analyses of efficacy. The mean change from baseline to endpoint will be summarized for the following efficacy endpoints.

- "Off" time as measured by the Parkinson's Disease Diary
- "On" time without troublesome dyskinesia (sum of "On" time without dyskinesia and "On" time with non-troublesome dyskinesia) as measured by the Parkinson's Disease Diary
- UPDRS total score, Parts I, II, III and IV scores, and dyskinesia item score
- PDQ-39 summary index and domain scores

For the analysis of change from baseline in efficacy measures, each subject's baseline will be their baseline measure in the first LCIG study in which they participated (e.g., Study S187.3.001, S187.3.002 or S187.3.004).

Additional Analysis

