8.5 Safety Analysis Variables

8.5.1 Adverse Events

Adverse event (AE) Investigator terms are assigned to a Lowest Level Term (LLT) and a Preferred Term (PT) and will be classified by High Level Term (HLT), High Level Group

Term (HLGT) to one System Organ Class (SOC), namely the primary SOC, according to the MedDRA thesaurus, Version 14.0.

AE Investigator terms that are related to procedural or device complications may also have a secondary coding. For example, consider the verbatim term "Worsening of Parkinson's disease due to PEG-J dislocation." This AE can be coded as follows:

Primary Coding –

- Lower Level Term: 'PARKINSONISM AGGRAVATED'
- Preferred Term: 'PARKINSONISM'
- System Organ Class: 'NERVOUS SYSTEM DISORDERS'

Secondary Coding –

- Lower Level Term: 'DEVICE DISLOCATION'
- Preferred Term: 'DEVICE DISLOCATION'
- System Organ Class: 'INJURY, POISONING AND PROCEDURAL COMPLICATIONS'

AE summaries will include the primary as well as the secondary coding.

A detailed description of each AE includes:

- The start and stop date of the event or "Ongoing" at the end of the study.
- Severity (categorized as "Mild," "Moderate" or "Severe"). If severity is missing it will be regarded as "Severe."
- Relationship to the investigational therapeutic system (categorized as "Unrelated," "Unlikely," "Possible" or "Probable").
- Action taken with investigational study medication:
 - Drug discontinued.
 - Drug interrupted.
 - Dosage reduced.

- Dosage increased.
- None/not applicable.
- Outcome of event, which is defined as any one of the following:
 - Recovered/Resolved.
 - Recovered/Resolved with Sequelae.
 - Fatal.
 - Unknown.

If an adverse event is "Ongoing," the Outcome will be blank.

- Serious, categorized as "Yes" or "No."
- Concomitant treatment/therapy introduced, categorized as "Yes" or "No."
- Led to study termination, categorized as "Yes" or "No."

Missing and/or incomplete dates for AEs are imputed in a manner resulting in the earliest onset within the Treatment Period and the longest duration. However, the Stop Date will not be imputed if the event is reported as "Ongoing."

Technically, this will be done as follows:

For a missing/incomplete start date the minimum of the following will be imputed:

- The maximum of the earliest possible start date and the date of first administration of investigational study drug
- The latest possible start date
- The latest possible stop date

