For a missing/incomplete stop date the maximum of the following will be imputed:

- The minimum of the latest possible stop date and the date of last administration of investigational study drug
- The earliest possible stop date
- The earliest possible start date

Here, the earliest (latest) possible date is defined as:

- The date itself if it is possible
- The date of the first (last) day of the month, if month and year are available but the day is missing
- The date of the first (last) day of the year, if year is available but day and month are missing
- A very early (late) date, for example, 01JAN1000 (01JAN3000), if the date is completely missing

From this data the following will be determined and used for presentation in the applicable tables and listings:

- Treatment-Emergent Adverse Events (TEAEs): Defined as AEs which started on or after the Date of the First 3005 LCIG Infusion and within 30 days of the Date of the Last 3005 PEG-J Exposure.
- Treatment-Emergent Serious Adverse Events (TESAEs): Defined as TEAEs regarded by the Investigator as Serious.
- TEAEs that are at least possibly related to the therapeutic system: Defined as TEAEs assessed as having a "Possible" or "Probable" relationship to the investigational therapeutic system and includes those events where the relationship is missing.
- Severe TEAEs: Defined as TEAEs assessed as being "Severe" in intensity and includes those events where the severity is missing.
- TEAEs that led to premature discontinuation: Selected as those events where: "Led to Study Termination" is indicated as "Yes."
- TEAEs with fatal outcome as reported on the "Adverse events" CRF.
- TEAEs in the following categories have been defined as TEAEs of special interest:
 - Procedure and device associated events
 - Polyneuropathy (broad search as well as narrow search)
 - Weight loss

- Cardiovascular fatalities
- Respiratory tract aspiration including aspiration pneumonia/pneumonitis

TEAEs are included in a category of special interest based on their PT and, in the case of cardiovascular fatalities, their outcome. The list of PT's assigned to each category is included as Appendix 12.4. Only TEAEs where an outcome of "Fatal" has been reported on the "Adverse Event" CRF are to be included in the category of cardiovascular fatalities. All events with PT's other than those assigned to the procedure and device associated AESI category will be included in summaries of events that are not procedure and device related.

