8.5.5.7 Neurological Examination

At each of the scheduled visits indicated in the flowchart of study assessments a neurological examination will be performed including light touch and pinprick sensation, vibratory sensation, deep tendon reflexes, and strength assessments. Any abnormalities or symptoms identified will be reported as adverse events.

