10058530	Peripheral nerve palsy	
10034591	Peripheral nervous system function test abnormal	
10054808	Peripheral paralysis	
10056673	Peripheral sensorimotor neuropathy	
10034620	Peripheral sensory neuropathy	
10034701	Peroneal nerve palsy	
10059923	Pharyngeal hypoaesthesia	
10036105	Polyneuropathy	
10036111	Polyneuropathy idiopathic progressive	
10036800	Progressive bulbar palsy	
10037114	Pseudobulbar palsy	
10049680	Quadriparesis	
10037714	Quadriplegia	
10037779	Radiculopathy	
10038254	Reflexes abnormal	
10038669	Respiratory arrest	
10038695	Respiratory failure	
10070833	Respiratory muscle weakness	
10038708	Respiratory paralysis	
10062162	Sensorimotor disorder	
10040026	Sensory disturbance	
10048871	Sensory integrative dysfunction	
10061567	Sensory level abnormal	
10040030	Sensory loss	
10041466	Speech disorder	
10061551	Spinocerebellar disorder	
10058560	Tandem gait test abnormal	
10068008	Trigeminal nerve paresis	
10049788	Trigeminal palsy	
10045380	Ulnar neuritis	
10045555	Unresponsive to stimuli	

Code	Preferred Term	Narrow Search (N)
10059101	Vibration test abnormal	
10050040	VII th nerve paralysis	
10047641	VI th nerve paralysis	
10071044	VI th nerve paresis	

Peripheral Neuropathy SMQ (20000034)

Code	Preferred Term	Narrow Search (N)
10066699	Acute polyneuropathy	N
10002027	Amyotrophy	N
10070439	Autoimmune neuropathy	N
10003882	Axonal neuropathy	N
10004846	Biopsy peripheral nerve abnormal	N
10067502	Decreased vibratory sense	N
10061811	Demyelinating polyneuropathy	N
10018767	Guillain-Barre syndrome	N
10051307	Ischaemic neuropathy	N
10057332	Loss of proprioception	N
10049567	Miller Fisher syndrome	N
10065579	Multifocal motor neuropathy	N
10028570	Myelopathy	N
10029175	Nerve conduction studies abnormal	N
10029223	Neuralgia	N
10029240	Neuritis	N
10071579	Neuronal neuropathy	N
10029331	Neuropathy peripheral	N
10034580	Peripheral motor neuropathy	N
10034591	Peripheral nervous system function test abnormal	N
10056673	Peripheral sensorimotor neuropathy	N
10034620	Peripheral sensory neuropathy	N
10036105	Polyneuropathy	N
10064135	Polyneuropathy chronic	N
10036111	Polyneuropathy idiopathic progressive	N

Code	Preferred Term	Narrow Search (N)
10068886	Radiation neuropathy	N
10062162	Sensorimotor disorder	N
10040026	Sensory disturbance	N
10040030	Sensory loss	N
10067722	Toxic neuropathy	N
10003084	Areflexia	
10056339	Autonomic failure syndrome	
10061666	Autonomic neuropathy	
10070237	Burning feet syndrome	
10006784	Burning sensation	
10013886	Dysaesthesia	

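### Neurological examination findings are recorded as adverse events without reference to the baseline examination, so existing signs with a missing or on-study onset date can be counted as treatment-emergent polyneuropathy

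*Protocol*

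**What the plan says.** Protocol 11.1.8 sets the recording rule: "Any abnormalities or symptoms identified during treatment will be recorded as adverse events". SAP 8.5.5.7 has nearly the same sentence, without the reference to treatment: "Any abnormalities or symptoms identified will be reported as adverse events". Neither limits the rule to new, worsened or clinically significant findings.

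The examination includes "assessment of tone, strength and abnormal movements", and also sensation, reflexes, coordination, gait and station. A baseline examination is scheduled: the Neurological Exam row of Protocol Table 2 carries footnote a, "The final assessment in the previous open-label LCIG study will serve as the baseline assessment for this item".

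The two documents define a TEAE differently. Protocol 13.3: "defined as any adverse event that begins or worsens in severity on or after the first dose of study drug in the current study". SAP 8.5.1: "Defined as AEs which started on or after the Date of the First 3005 LCIG Infusion". The SAP leaves out worsening, and SAP 10.1 does not list this as a change. On dates, SAP 8.5.1 says: "Missing and/or incomplete dates for AEs are imputed in a manner resulting in the earliest onset within the Treatment Period".

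Polyneuropathy is an adverse event of special interest (AESI). SAP 8.5.1 assigns events to it by preferred term, using the lists in SAP 12.4. The narrow list includes "Decreased vibratory sense".

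**The concern.** Advanced Parkinson's disease brings abnormal neurological signs with it. SAP 8.2.3.2 records rigidity, rest tremor and postural instability as diagnostic features at initial screening. Some subjects may also enter with stable sensory loss. A rule that takes any abnormality, repeated every 6 months, does not tell the site to separate what was already there from what is new.

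Other assessments in the plan do have a filter. Protocol 11.1.7 sends only relevant physical findings to the AE form. Protocol 11.1.10 notes change from the previous ECG. SAP 8.5.2 and 8.5.3 require a potentially clinically significant laboratory or vital sign value to be more extreme than baseline.

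Two outputs are at stake. The first is the polyneuropathy AESI, in Table 14.3__1.2.2.12 (broad) and Table 14.3__1.2.2.13 (narrow). The second is the Narrow Polyneuropathy Subset of SAP 8.1.1, which is defined by narrow-term TEAEs and is used to study the association with vitamin deficiency. Prevalent sensory loss in that subset would blur the association. SAP 9.11.5 names the neurological examination among its analyses, but the only output in SAP 12.2 and 12.3 is listing NEL001. No current table separates existing from new findings.

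**Working it through.** The documents give no figure to reproduce, so the check has three parts.

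**1. Which existing signs pass the TEAE date test?** SAP 8.5.1 gives:

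imputed start = min{ max(earliest possible start, first dose), latest possible start, latest possible stop }

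The TEAE test is then start ≥ Day 1. Take an example Day 1 of 15 Jun 2011 and a sign that is still ongoing, so the stop date does not bind.

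| Onset as entered | Calculation | Start used | TEAE? |
|---|---|---|---|
| 10 Mar 2009, complete | none needed | 10 Mar 2009 | No |
| Year 2009 only | min{max(1 Jan 2009, 15 Jun 2011), 31 Dec 2009} | 31 Dec 2009 | No |
| Year 2011 only | min{max(1 Jan 2011, 15 Jun 2011), 31 Dec 2011} | 15 Jun 2011 | Yes |
| Jun 2011 only | min{max(1 Jun 2011, 15 Jun 2011), 30 Jun 2011} | 15 Jun 2011 | Yes |
| Wholly missing | min{max(1 Jan 1000, 15 Jun 2011), 1 Jan 3000} | 15 Jun 2011 | Yes |
| Examination date, 12 Dec 2011 | none needed | 12 Dec 2011 | Yes |

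A stable baseline sign is therefore counted in three situations: the examination date is entered as onset, the onset is missing, or a partial onset covers the month or year of Day 1. In the last two, the SAP assigns Day 1 even when the baseline examination already shows the sign.

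**2. Which category does it reach?** From SAP 12.4:

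- Narrow list: decreased vibratory sense, loss of proprioception, sensory loss, sensory disturbance.
- Broad list only: gait disturbance, muscular weakness, areflexia, hyporeflexia, coordination abnormal, balance disorder, tandem gait test abnormal.

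Existing sensory findings can thus reach the narrow category and the subset. Existing gait, strength, reflex or coordination signs can reach only the broad category.

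**3. How large could it be?** Let q be the true new-onset proportion, b the proportion with an existing sign and no new event, and f the share of those signs that pass the date test. Then reported proportion = q + b × f. The planned N of about 275 is in Protocol 7.1. The values of q, b and f are assumptions. With q = 5% (0.05 × 275 = 13.8 subjects):

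| f | b = 10% | b = 40% |
|---|---|---|
| 0 | 5.0% (13.8) | 5.0% (13.8) |
| 0.25 | 7.5% (20.6) | 15.0% (41.3) |
| 0.5 | 10.0% (27.5) | 25.0% (68.8) |
| 1 | 15.0% (41.3) | 45.0% (123.8) |

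Under a new-or-worsened rule f = 0, and the reported proportion equals q.

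**The case against.** The strongest reply is that recording a sign as an AE does not make it a TEAE. Both definitions test onset, so a sign entered with its true pre-study date stays out of the AESI tables and of the subset. This stands. A reader might infer from the recording rule that existing Parkinson's signs become TEAEs as a matter of course, or that nearly every subject would be counted. The documents do not support that: the date test excludes correctly dated signs, the examination is done during On time, and subjects enter with a good therapeutic response. A reader might also expect rigidity and tremor to feed the AESI, but neither is on the polyneuropathy lists.

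It can also be said that the protocol wording may mean first identified during treatment, that Protocol 12.1.1 asks for signs of one diagnosis to be grouped under one term, and that earlier findings belong in the history forms. These soften the point without removing it. The SAP sentence has no reference to treatment. The history forms cover only what was reported at initial screening, before the first LCIG study (SAP 6.4.2 and 8.2.3.1). Neither document says which onset date to enter for a sign present at baseline.

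Finally, broad capture is deliberate: Protocol 12.1.4 makes possible precursors of polyneuropathy an AESI. That is a sound reason to collect widely and not to discard worsened findings. It is not a reason to count an unchanged baseline sign as treatment-emergent. The shift summaries that appear as superseded text in the amendment log are not counted here as an error.

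**Conclusion.** The point holds as a risk that depends on dating. The recording rule ignores the baseline examination, and the SAP imputation can turn a sign known to predate Day 1 into a TEAE. The narrow category and the subset are exposed through sensory findings only; the broad category is exposed through gait, strength, reflex and coordination signs as well.

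The size cannot be derived from the documents. They give neither the prevalence of such signs at entry nor how sites dated them, and the percentages above only show how strongly the result depends on f.

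There is also an error in the other direction. Because the SAP definition omits worsening, a sign that worsens on study under its original pre-Day 1 onset is missed, although Protocol 13.3 would count it.

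The point deserves action because long-term safety is the primary statistical objective (Protocol 13.1) and polyneuropathy is a named AESI.

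**What to change.** - **Protocol 11.1.8 and SAP 8.5.5.7:** record as an AE a finding that is new or worse than the baseline neurological examination. State that a sign present at baseline keeps a pre-Day 1 onset unless it worsened.
- **SAP 8.5.1:** do not impute onset to Day 1 when the baseline examination already shows the abnormality. Count worsening as treatment-emergent, as Protocol 13.3 does.
- **Data already collected:** flag polyneuropathy TEAEs whose abnormality was present and no worse at baseline. Show Tables 14.3__1.2.2.12 and 14.3__1.2.2.13 and the Narrow Polyneuropathy Subset with and without the flagged events. Do not drop worsened findings.
- **Subjects without a baseline examination:** show them separately. The Amendment 1 schedule in SAP 12.1.1 has no neurological examination and the Amendment 2 schedule does, and the documents do not say whether the previous studies collected one. Using the first 3005 examination as a clean reference could hide neuropathy that arose on LCIG.

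The cost is a short wording change in each document and one flag built from examination data already scheduled. The documents describe no link between examination results and coded AE terms, so the matching will need some manual review.

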11.1.9 Laboratory Evaluations

The laboratory evaluations listed in Table 1, including special tests for vitamin deficiencies (Folic Acid, Vitamin B6, Vitamin B12, Methylmalonic Acid (MMA), and Homocysteine) will be performed by a central laboratory to be designated by Sponsor, at the times indicated in [Table 2](#). No other formal assessment of laboratory evaluations is scheduled, but will be done as subject's condition mandates and performed as an element of routine care.

Table 1. Laboratory Evaluations

Hematology	Blood Chemistry	Special Tests	Urinalysis
Hemoglobin	Glucose	Folic Acid,	pH
Hematocrit	Creatinine	Vitamin B6,	Specific Gravity
White blood count	Creatinine kinase	Vitamin B12,	Glucose
(WBC) with differential	Alkaline phosphatase	Methylmalonic Acid	Protein
Erythrocyte count (RBC)	Total bilirubin	(MMA), and	Microscopic
Platelet count	Serum glutamic-	Homocysteine levels	Examination
Mean corpuscular volume	pyruvic transaminase		Urine Pregnancy
(MCV)	(SGPT/ALT)		Test -
Mean corpuscular	Serum glutamic-		For subjects who are
hemoglobin (MCH)	oxaloacetic		of child-bearing
Mean corpuscular	transaminase		potential, a negative
hemoglobin	(SGOT/AST)		urine pregnancy test
concentration (MCHC)	Gamma-glutamyl		is required on the
	transpeptidase		day of the procedure
	(GGT)		prior to any
	Total protein		radiological check
	Uric acid		of tube placement.
	Calcium		
	Sodium		
	Potassium		
	Chloride		
	Serum urea nitrogen		
	(BUN)		
	Bicarbonate		
	Lactate dehydrogenase		
	(LDH)		
	Total cholesterol		
	Triglycerides		
	Albumin		
	Pregnancy Test for		
	applicable subjects ^a		
	Beta human chorionic		
	gonadotropin		
	(β -hCG)		

a. For all females of child-bearing potential, at end of study.

